3.2 Exclusion Criteria

- 3.2.1 History of severe hypersensitivity reaction (eg. anaphylaxis) to other biologic drugs or monoclonal antibodies
- 3.2.2 Clinically significant cardiac disease or impaired cardiac function, including any of the following:
 - Clinically significant and/or uncontrolled heart disease such as congestive heart failure (New York Heart Association grade ≥ 2), uncontrolled hypertension, or clinically significant arrhythmia currently requiring medical treatment
 - QTcF > 470 msec on screening electrocardiogram (ECG) or congenital long QT syndrome. NOTE: If the initial automated QTcF interval is > 470 msec at screening, for the purpose of determining eligibility, the mean QTcF, based on at least 3 ECGs obtained over a brief time interval (ie, within 30 minutes), should be manually determined by a medically qualified person.
 - Acute myocardial infarction or unstable angina pectoris < 6 months prior to Screening
- 3.2.3 Presence of symptomatic or untreated central nervous system (CNS) metastases, or CNS metastases that require doses of corticosteroids within the prior 3 weeks to study Day 1. Patients with brain metastases are eligible if lesions have been treated with localized therapy and there is no evidence of progression for at least 4 weeks by MRI prior to the first dose of study drug
- 3.2.4 Active infection requiring systemic antibiotic therapy. Patients requiring systemic antibiotics for infection must have completed therapy at least 1 week prior to the first dose of study drug
- 3.2.5 Known history of uncontrolled human immunodeficiency virus (HIV) infection (defined as CD4 count < 200 and/or a detectable viral load). Testing for HIV status is not necessary unless clinically indicated

- 3.2.6 Active hepatitis B virus (HBV) or hepatitis C virus (HCV) infection per institutional protocol. Testing for HBV or HCV status is not necessary unless clinically indicated or the patient has a history of HBV or HCV infection
- 3.2.7 Malignant disease, other than that being treated in this study. Exceptions to this exclusion include the following: malignancies that were treated curatively and have not recurred within 2 years prior to study treatment; completely resected basal cell and squamous cell skin cancers; any malignancy considered to be indolent and that has never required therapy; and completely resected carcinoma in situ of any type
- 3.2.8 Any medical condition that would, in the investigator's or Sponsor's judgment, prevent the patient's participation in the clinical study due to safety concerns, compliance with clinical study procedures or interpretation of study results
- 3.2.9 Patients receiving systemic steroid therapy or any other immunosuppressive medication at any dose level, as these may interfere with the mechanism of action of study treatment. Local steroid therapies (eg, otic, ophthalmic, intra-articular or inhaled medications) are acceptable
- 3.2.10 History of adrenal insufficiency
- 3.2.11 Participants with clinically significant pulmonary disease or impaired lung function, including any of the following:
- An oxygen saturation of < 92% on room air, measured by pulse oximeter
 - History of interstitial lung disease
 - History of pneumonitis that required corticosteroid treatment or current pneumonitis
 - Ongoing requirement for intermittent or continuous oxygen supplementation
- 3.2.12 History of colitis or inflammatory bowel disease
- 3.2.13 Major surgery within 2 weeks of the first dose of study drug (minimally invasive procedures such as bronchoscopy, tumor biopsy, insertion of a central venous access device, and insertion of a feeding tube are not considered major surgery and are not exclusionary)
- 3.2.14 Radiotherapy within 2 weeks of the first dose of study drug, with the exception of palliative radiotherapy to a limited field, such as for the treatment of bone pain or a focally painful tumor mass
- 3.2.15 Use of hematopoietic colony-stimulating growth factors (eg, G-CSF, GM-CSF, M-CSF) ≤ 2 weeks prior to start of study drug. An erythroid-stimulating agent is allowed as long as it was initiated at least 2 weeks prior to the first dose of study treatment and the patient is not red blood cell transfusion dependent

- 3.2.16 Women who are pregnant or nursing/breastfeeding. Where pregnancy is defined as the state of a female after conception and until the termination of gestation.
- 3.2.17 Women of childbearing potential who are sexually active with a non-sterilized male partner, defined as all women physiologically capable of becoming pregnant, unless they are using highly effective contraception during study treatment (defined in Section 7.2.3), and must agree to continue using such precautions for 6 months after the final dose of investigational product; cessation of birth control after this point should be discussed with a responsible physician.
- 3.2.18 Male patients must be surgically sterile or use double barrier contraception methods from enrollment through treatment and for 6 months following administration of the last dose of study drug

3.3 Inclusion of Women and Minorities

Men, women, and members of all ethnic and racial groups are eligible for this trial.

4. REGISTRATION PROCEDURES

4.1 General Guidelines

After obtaining Informed Consent, eligible patients will be enrolled on this trial. Subjects will be registered by local sites through an electronic database and will be issued a subject unique identifying numbers for eligible participants. An investigator is required to prepare and maintain adequate and accurate case histories designed to record all observations and other data pertinent to the investigation on each subject treated with the investigational product in the study or registered to the study. SARC may request faxed copies of selected source documents with PHI redacted for verification of records, accuracy of electronic submissions and review of data.

While all study evaluations must be performed by the Investigator as described in Section 10, Study Evaluations and Study Calendar, only data related to the primary and secondary endpoints, as well as safety data, will be captured in the eCRFs.

4.2 Registration Process

This study uses a web based data entry system for data submission. All subject registrations and Case Report Forms (CRFs) will be submitted electronically via the study web site. All subjects must be registered on the study website prior to start of treatment. Data Managers and other authorized users will be provided with a unique user identification number and password to access the site. All study case report forms may be accessed online through the study website. In case there are problems accessing the website, please contact the SARC office directly at: [contact].

4.3 Central Pathology Review

5. TREATMENT PLAN

Pre-screening

Patients with a diagnosis of unresectable or metastatic CCS who are considered for this study will first enter the pre-screening study phase. Patients will sign a pre-screening informed consent form and undergo HLA testing in a CLIA-certified laboratory (unless this has already been done as a part of the patient's routine oncologic care). Patients who are HLA-A*02:01 will be eligible to sign consent for the interventional portion of this study and may initiate treatment after the screening phase. Patients who are HLA-ineligible will be offered the opportunity to participate in an observational study to track clinical outcomes with physician's choice of therapy.

Screening and Treatment

HLA-A*02:01 positive patients who are eligible to participate after completing screening assessments will begin tebentafusp treatment on C1D1 and C1D8 at 20 mcg and 30 mcg per week, respectively. The majority of moderate-to-severe toxicity associated with tebentafusp in previous studies were observed at these 2 dose time points and included hypotension, rash, pruritus, fever, and chills. After this initial dosing period, beginning at C1D15 and beyond, patients will receive the full dose of 68 mcg. This escalated dose administered at C1D15 will be the dose used for the remainder of the treatment period. Beginning with C1D8, tebentafusp will be administered on the scheduled day (\pm 2 days), and consecutive infusions of tebentafusp must be administered at least 5 days apart. A treatment cycle is defined as 21 days for the purposes of scheduling procedures and evaluations. Please refer to Section 11.0 for details of the timing of required assessments.

The first six patients treated with tebentafusp will require overnight hospitalization and a minimum of pre-dose and Q4-hour vital signs monitoring after the first administration of tebentafusp (C1D1), the second administration (C1D8), and the third escalated dose of tebentafusp (C1D15) is administered. For the first 3 administrations of tebentafusp, patients must be monitored for at least 16 hours after dosing.

If no Grade \geq 2 episodes of cytokine release syndrome or Grade \geq 3 infusion-related reactions among the first six patients treated with tebentafusp, subsequent patients may be treated with tebentafusp in either an inpatient or an outpatient setting for the first three study doses, at the discretion of the treating physician. Additional information regarding this 'de-escalation' of monitoring can be found in Section 5.1.3

During the course of the study visits, tests and/or procedures should occur on schedule whenever possible. A visit window of \pm 2 days is allowed for all visits where study drug administration is scheduled. For all other visits, a visit window of \pm 7 days is allowed, unless otherwise indicated. If the study drug infusions are delayed or otherwise moved from the scheduled day, all study assessments will be moved with the delayed study drug infusions. The only exception to moving study assessments with treatment are the radiological assessments, which must be performed \pm 7 days of the scheduled date of the assessment (unless otherwise indicated) taking as reference C1D1. The protocol specified

radiologic assessments should be performed as scheduled every 6 weeks as indicated in the protocol (reference to C1D1) and should not follow delays incurred in the treatment period for the accurate assessment of PFS and duration of response endpoints. Radiologic assessments should not move if delays in treatment are incurred.

Patients will be treated until they experience unacceptable toxicity, disease progression and/or treatment is discontinued at the discretion of the investigator or the patient, as described in Section 5.3.

Patients receiving tebentafusp who have radiologic evidence of disease progression by RECIST and have evidence of clinical benefit, such as disease shrinkage at other sites or symptomatic improvement, may continue treatment with tebentafusp after discussion with the Principal Investigator and re-consent (Section 12). Patients who continue on treatment after disease progression should discontinue study treatment once they have unequivocal, confirmed progression or are no longer deriving benefit as assessed by the investigator.

5.1 Agent Administration

5.1.2 Rationale for intra-patient escalation regimen

Several key observations in the first-in-human Phase I study of tebentafusp (IMCgp100-01) led to the intra-patient escalation regimen. First, the identified RP2D of the weekly dosing regimen at 50 mcg led to severe toxicity at the first or second dose in a cohort of patients with uveal melanoma in the expansion cohort. The basis for the enhanced toxicity is the high expression level of the gp100 antigen in uveal melanoma, profound lymphocyte trafficking into skin and tumor, as well as the extent of disease in these patients. From this observation, the intra-patient escalation regimen was tested with a low fixed dose at C1D1 (20 mcg) and C1D8 (30 mcg) followed by resumption of dosing at the RP2D of 50 mcg at C1D15 and beyond. This regimen was well tolerated in a subsequent cohort of patients with uveal (n=6) and cutaneous (n=1) melanoma. A review of the efficacy data from this Phase I study revealed that patients with more extensive disease had demonstrated PRs generally at doses higher than the defined RP2D of 50 mcg and specifically in uveal melanoma, the PRs were observed doses of 48–81 mcg. The Phase I of the intra-patient escalation regimen was initiated (study IMCgp100-102), to both avoid the infusion-related toxicity at Weeks 1 and 2 and to increase the exposure of IMCgp100 closer to those doses where PR were observed in uveal melanoma.

Preclinical data suggests that the residence time of tebentafusp to the HLA-A*02:01 allele is considerably longer resulting in enhanced effects compared to non-HLA-A*02:01 alleles. This is borne out in the clinical data, where patients expressing non-HLA-A*02:01 alleles appear to have fewer T cell mediated toxicities and no clinical responses have been observed. Given these preclinical and clinical data, enrollment is therefore limited to patients expressing the HLA-A*02:01 allele.

In Study IMCgp100-102, patients with advanced uveal melanoma were treated with the intra-patient escalation regimen of 20 mcg at C1D1, 30 mcg at C1D8, followed by an

escalated dose at C1D15 and beyond. To identify the escalated dose for C1D15 and beyond, a conservative escalation approach was taken (Cohort 1 at 54 mcg, Cohort 2 at 64 mcg, and escalating in increments of approximately 10 mcg). A dose level of 73 mcg was not tolerated due to elevations in hepatic transaminases with a concurrent low-grade increase in bilirubin in 2 of 4 treated patients; these events were reversible without administration of corticosteroids and all patients who experienced DLTs remained on treatment. After a dose reduction to 68 mcg, 6 patients were treated with no DLTs and no significant liver enzyme elevations. A dose of 68 mcg was identified as the MTD and was selected as the dose level for further study of the intra-patient escalation regimen.

Tebentafusp monotherapy will be administered as an intravenous (IV) infusion over 15 to 20 minutes at the standard regimen of 20 mcg on Week 1, 30 mcg on Week 2, 68 mcg on Week 3, and 68 mcg once weekly thereafter. This is the same regimen used in the randomized Phase 3 study (IMCgp100-202) in uveal melanoma and demonstrated a strong risk/benefit with an HR for OS of 0.51 and a low rate of treatment-related AEs resulting in discontinuation (2%).

5.1.3 Escalation Regimen

All patients will receive treatment with single-agent tebentafusp on C1D1 and C1D8 at 20 mcg and 30 mcg per week, respectively. The majority of moderate-to-severe toxicity associated with tebentafusp is observed at these 2 dose time points and has typically included hypotension, rash, pruritus, fever, and chills. After this initial dosing period, beginning at C1D15 and beyond, patients will receive the escalated dose of 68 mcg. This escalated dose administered at C1D15 will be the dose used for the remainder of the treatment period. Beginning with C1D8, tebentafusp will be administered on the scheduled day (\pm 2 days), and consecutive infusions of tebentafusp must be administered at least 5 days apart.

For the first six patients treated, this intra-patient escalation regimen requires overnight hospitalization and a minimum of pre-dose and Q4-hour vital signs monitoring after the first administration of tebentafusp (C1D1), after the second administration (C1D8), and after the escalated dose of tebentafusp on C1D15 is administered. For the first 3 administrations of tebentafusp, patients should be monitored for at least 16 hours after dosing. “Inpatient hospitalization” refers to a facility with fully functional resuscitation facilities, 24-hour monitoring, and physician availability. See Section 10.4 for additional details on vital signs monitoring.

Inpatient monitoring at C2D1 will be determined by the toxicity observed in the C1D1–C1D15 doses as follows:

1. If the escalated dose at C1D15, administered as an inpatient, does not raise safety concerns (and the patient does not experience an adverse reaction involving hypotension of grade \geq 2), the subsequent dose at C2D1 and all subsequent doses can be administered on an outpatient basis.

2. If the patient experiences hypotension requiring any medical intervention (National Cancer Institute Common Terminology Criteria for Adverse Events [NCI CTCAE] grade ≥ 2) at C1D15, then the C2D1 dose should be administered with inpatient monitoring, similar to C1D1–C1D15. If the patient does not experience hypotension requiring medical intervention at the C2D1 dose administered as an inpatient, then all subsequent doses can be administered on an outpatient basis.
3. Hospitalization at other days (eg, Cycle 2 and beyond) is determined at the discretion of the principal investigator based on the patient's history and tolerance for the initial doses of the study medication, with the exception of patients experiencing a treatment delay (please refer to bullet 4 below).
4. Patients experiencing a break or delay in treatment for any reason of more than 2 weeks AND with a history of a grade 3 or 4 event of hypotension with tebentafusp dosing during the first weeks of treatment will be monitored as an inpatient for the dose subsequent to the break in dosing, regardless of the timing of the break in dosing, with vital signs monitored at a minimum of every 4 hours and monitoring for at least 16 hours after dosing.

If none of the first six patients experience **Grade ≥ 2 CRS or Grade ≥ 3 infusion-reactions**, subsequent patients can be treated as an outpatient for their intra-patient dose escalation. However, all patients undergoing intra-patient dose escalation require monitoring in a facility with access to resuscitation equipment, rescue medications, and physician availability. Patients must be monitored for at least 8 hours post-end of infusion on C1D1, C1D8, and C1D15. Vital signs must be confirmed stable prior to discharge. Minimum thresholds are body temperature $< 38.2^{\circ}\text{C}$, heart rate < 110 beats per minute, and oxygen saturation 92% on room air.

Antihypertensive drugs are allowed as concomitant medications; however, because transient hypotension has occurred during infusions of monoclonal antibodies and ImmTACs, the investigators should consider reducing or not administering antihypertensives for 24 hours before and after the tebentafusp administration during at least the first 3 weeks of treatment. Appropriate management of patients, especially those with more severe hypertension, receiving medications that may cause rebound hypertension when abruptly discontinued or those who are on multiple blood pressure medications should be discussed with a cardiology consultant and the Principal Investigator.

In addition, due to the risk of hypotension, IV fluids may be administered prior to tebentafusp administration and, if given, IV fluids will be recorded as a concomitant medication. The administration of IV fluids should be guided by clinical evaluation and the volume status of the patient. Pruritus is a common AE with tebentafusp, so premedication with an antihistamine may be considered. See Appendix 18.1 for further recommendations regarding treatment of skin toxicity. If a patient experiences an infusion reaction, he/she may receive premedication on subsequent dosing days after consultation with the Principal Investigator. Pre-medications should include, but are not

limited to, paracetamol/acetaminophen and antihistamine. Corticosteroid premedication should be avoided; corticosteroids should only be considered if the paracetamol/acetaminophen and antihistamine combination is not effective.

Acute allergic reactions should be treated as needed using institutional guidelines. In the event of anaphylactic/anaphylactoid reactions, any therapy necessary to restore normal cardiopulmonary status should be implemented immediately. Such acute allergic reactions will be reported to the Sponsor in an expedited manner. These should be designated as reportable as an SAE, regardless of hospitalization, as medically important events. Please refer to the SAE reporting section for details. The individual symptoms of the infusion-related reaction should be captured in order to best characterize the study drug infusion reactions, unless the investigator considers another category, such as “allergic reaction” or “anaphylaxis,” more appropriate in a specific situation.

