Anti-hypertensives are allowed as concomitant medications; however, because transient hypotension has occurred during infusions of tebentafusp and monoclonal antibodies, treatment with anti-hypertensive therapy should be held for 24 hours before and 24 hours after tebentafusp in the first 6 weeks of treatment, and thereafter, at the discretion of the principal investigator. Medications administered as supportive care of bony metastases, including bisphosphates and denosumab, may be administered during study therapy.

Treatment with palliative radiotherapy to tumor locations to alleviate pain is acceptable during the course of the study provided that: (1) with bony lesions, no new bone lesions are noted (representing clinically significant progression of disease) and (2) only non-target lesions are radiated. Radiation of target lesions is not permitted while receiving study treatment.

Prohibited Therapy

While on study treatment, patients may not receive other additional investigational study drugs, agents, devices, chemotherapy, or any other therapies that may be active against cancer. As described above, palliative radiotherapy or surgery is allowed and bisphosphonates may be given for bone metastases. Additionally, no other therapeutic monoclonal antibodies, except for denosumab and tocilizumab if required for patient care, and no immunosuppressive medication may be administered while on this study, unless prescribed to manage toxicity as recommended in Appendix B. While systemic corticosteroid therapy will interfere with the mechanism of action of the study medications, its use is recommended in some settings. Live or attenuated vaccines are prohibited from 28 days prior to the first dose until 30 days after the final dose of the study drug.

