Patients with adrenal insufficiency or patients receiving systemic steroid therapy or any other immunosuppressive medication at any dose level at Screening are excluded. Patients receiving corticosteroids may not be able to mount an appropriate physiologic cortisol response in the event of an infusion reaction with initial tebentafusp dosing. Corticosteroids and other immunosuppressives may interfere with the mechanism of action of the study drugs. The use of systemic corticosteroid therapy is permitted/recommended in the following settings: (1) infusion reactions and (2) immune-mediated toxicities and toxicity management (eg, hypotension and CRS) as directed in Appendix B (eg, hypotension not resolving with fluid support alone). Of note, patients with a pre-existing history of adrenal insufficiency are excluded from study participation. Any additional uses of systemic corticosteroid therapy during the study should be discussed with the Principal Investigator.

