7.3 Warnings and Precautions

7.3.1 Cytokine Release Syndrome

Cytokine release syndrome is a class effect of all T cell engagers and is due to an immune cascade following T cell activation. The tebentafusp regimen did not mandate prophylactic corticosteroids, antihistamines, or acetaminophen prior to dosing. Cytokine release syndrome was programmatically adjudicated using the ASTCT consensus grading for CRS (Lee, 2019). As of the DCO for this IB update, 344 (88.0%) of the 505 patients who received tebentafusp monotherapy across all clinical studies, experienced an AE of CRS that was considered related to study drug.

In IMCgp100-202 Study, which forms the largest dataset of programmatically derived CRS events, approximately 89% of patients following tebentafusp administration experienced CRS.

Most patients had Grade 1 (12%) or Grade 2 (76%) CRS. The incidence of Grade 3 CRS was 0.8%. There were no Grade 4 CRS or death due to CRS. The diagnosis of CRS following tebentafusp infusion was based most frequently on pyrexia followed by hypotension and infrequently hypoxia. Other commonly observed symptoms with CRS included chills, nausea, vomiting, fatigue, and headache.

Most patients experienced CRS following each of the first 3 tebentafusp infusions, with decreasing severity and frequency. In the majority of cases, CRS started on the day of infusion. Pyrexia was noted in nearly all cases of CRS, and in these patients, an increase in body temperature generally occurred within the first 8 to 10 hours after tebentafusp infusion. Cytokine release syndrome rarely (1.2%) led to treatment discontinuation. Cytokine release syndrome should be managed per the institutional protocol for CRS. In the absence of an institutional protocol, management guidance for hypotension and CRS with fluid management and IV corticosteroids has been included in all study protocols with tebentafusp. Based on the observed toxicities during the early weeks of dosing (eg,

hypotension), specific recommendations for close observation of subjects are included in each of the clinical study protocols.

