Grade 3 or 4	
Discontinue tebentafusp infusion immediately and permanently discontinue participant from study treatment.
 
NOTE: Grade 3 infusion-related reactions that improve by at least 1 grade within 6 hours of onset will not require permanent discontinuation. If treatment is continued, all guidance provided for the management of Grade 2 reactions must be followed.
 
Manage severe infusion-related reactions per institutional standards. Provide supplemental oxygen, fluids, and other resuscitative measures as needed. Monitor vital signs (eg, BP, pulse rate, respiration rate, temperature, and oxygen saturation) until resolution.

Infusion-Related Reactions/Cytokine Release Syndrome (occurring after infusion/injection; graded per ASTCT 2019, see Table 6)	

Grade 1	
 Admit for inpatient monitoring (unless already hospitalized per protocol). Assess for potential infection and treat fever and neutropenia. Manage according to individual symptoms. Treat symptomatically as indicated, including antihistamines, antipyretics, antiemetics, and/or analgesics as needed. Initiate bolus and/or maintenance IV fluids and carefully monitor fluid balance. Vigilantly monitor for escalation to Grade 2 CRS with frequent vital signs monitoring (eg, assess vital signs every 2 hours) Strongly consider early, high dose corticosteroid therapy if there is progressive worsening of vital signs (see Grade 2 below). Consider prophylactic electrolyte supplementation for participants receiving IV fluids with low-normal serum electrolyte levels. 
Once symptoms resolve, at the next dose, do the following:
 
 If at 20 or 30 mcg dose, may escalate to next dose level. If at 68 mcg, continue at this dose level

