Grade 2	
 Increase monitoring with continuous cardiac and pulse oximetry monitoring and continue or increase vital signs monitoring (eg, assess vital signs every hour). To manage hypotension, administer bolus IV fluids (recommended rate of approximately 1 L per hour) and supplemental oxygen for hypoxia or respiratory distress. If not rapidly resolved (ie, within 2-3 hours of onset) with fluids and/or supplemental oxygen, administer high dose IV corticosteroid therapy (eg, methylprednisolone 1 to 2 mg/kg initial dose or equivalent) and/or tocilizumab 8 mg/kg IV (not to exceed 800 mg/infusion) per institutional guidelines until symptoms (eg, hypotension) resolve. Consider prophylactic electrolyte supplementation for participants receiving IV fluids with low-normal serum electrolyte levels. Consider additional respiratory support as needed to manage ongoing or persistent respiratory distress. 
Once symptoms resolve, at the next dose, do the following:
 
 Administer corticosteroid premedication (eg, dexamethasone 4 to 12 mg or equivalent) at least 30 minutes prior to the next dose If at 20 or 30 mcg dose, may escalate to next dose level. If at 68 mcg, continue at this dose level; monitor for at least 16 hours post-dose

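### Section 5.1.3 and Appendix B give opposite instructions on corticosteroid premedication after an infusion-related reaction or CRS, and no text reconciles them; the antihypertensive rules also differ, as a smaller item

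*Protocol*

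**What the plan says.** **Steroid premedication.** Section 5.1.3 of the Protocol opens the subject with "If a patient experiences an infusion reaction, he/she may receive premedication on subsequent dosing days after consultation with the Principal Investigator". It names acetaminophen and an antihistamine as the premedication to include, and then adds "Corticosteroid premedication should be avoided; corticosteroids should only be considered if the paracetamol/acetaminophen and antihistamine combination is not effective".

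Appendix B has a row headed "Infusion-Related Reactions/Cytokine Release Syndrome (occurring after infusion/injection; graded per ASTCT 2019, see Table 6"). Its Grade 2 and Grade 3 entries give the same instruction for the dose that follows: "Administer corticosteroid premedication (eg, dexamethasone 4 to 12 mg or equivalent) at least 30 minutes prior to the next dose". Neither entry makes this depend on failure of a non-steroid combination. The Grade 3 entry requires written approval from the Medical Monitor before restarting.

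**Why steroids matter to this drug.** Section 5.2 says "Corticosteroids and other immunosuppressives may interfere with the mechanism of action of the study drugs". Elsewhere the same section puts it more firmly, as something systemic steroids will do, while allowing them for toxicity management as set out in Appendix B.

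**Expected CRS.** For IMCgp100-202, Section 7.3.1 reports "Most patients had Grade 1 (12%) or Grade 2 (76%) CRS. The incidence of Grade 3 CRS was 0.8" per cent.

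**Antihypertensives.** Section 5.1.3 says "the investigators should consider reducing or not administering antihypertensives for 24 hours before and after the tebentafusp administration during at least the first 3 weeks". Section 5.2 says "treatment with anti-hypertensive therapy should be held for 24 hours before and 24 hours after tebentafusp in the first 6 weeks of treatment", and leaves the matter to discretion after that.

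**The concern.** Consider a patient with Grade 2 CRS after the first dose. A site working from Section 5.1.3 would avoid steroid premedication at the second dose unless acetaminophen plus antihistamine had proved ineffective. A site working from Appendix B would give it. Both could say they had followed the protocol.

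Section 7.3.1 reports that most patients had CRS after each of the first three infusions, so the conflict would arise during the dose escalation. Two things are at stake. One is consistent prevention of a risk listed among the special warnings. The other is consistent conditions of drug exposure, since the protocol itself holds that steroids can interfere with the mechanism of action.

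The antihypertensive rules raise the same kind of problem for the related risk of hypotension, but only for patients who take those drugs.

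**Working it through.** **Step 1. Steroid rules side by side.**

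| | Section 5.1.3 | Appendix B, Grade 2 and 3 CRS |
|---|---|---|
| Trigger | An infusion reaction, no grade or timing given | CRS after infusion, in a row also titled infusion-related reactions |
| Steroid before next dose | To be avoided | To be administered |
| Precondition | Non-steroid combination not effective | None stated |

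The triggers overlap because Appendix B itself files CRS under infusion-related reactions and Section 5.1.3 sets no limit by grade or timing. On whether to give the steroid, the instructions are opposite.

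**Step 2. Does any text settle precedence?** Section 5.2 permits immunosuppressive drugs when used for toxicity as Appendix B recommends, and permits or recommends systemic steroids for infusion reactions and for CRS. Section 6 refers the reader to Appendix B for adverse event management. None of these mentions the premedication sentence in Section 5.1.3, withdraws it or limits it to particular events. In the paragraph concerned, Section 5.1.3 does not cite Appendix B. For skin toxicity it cites an Appendix 18.1, whereas the contents list only Appendices A and B.

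**Step 3. Reproduce the protocol's CRS rate.** The Section 7.3.1 grades for IMCgp100-202 are 12%, 76% and 0.8%, with no Grade 4. Their sum is 12 + 76 + 0.8 = 88.8%, which agrees with the stated figure of approximately 89%.

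**Step 4. Patients who would meet the Appendix B trigger.** Number = 23 × P(Grade 2 or 3 CRS), with 23 patients in the tebentafusp arm.

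- IMCgp100-202 rates carried over (assumption): 0.76 + 0.008 = 0.768; 23 × 0.768 = 17.7, about 18 of 23.
- Half that rate (assumption): 0.384; 23 × 0.384 = 8.8, about 9 of 23.
- Intermediate case: Section 7.3.1 also gives a pooled count of 344 of 505, printed as 88.0%. The quotient is 344/505 = 68.1%; a rate of 88.0% would need a denominator of about 344/0.88 = 391. Taking 68.1% for any-grade CRS and keeping the IMCgp100-202 grade mix (assumption): 0.681 × 76.8/88.8 = 0.589; 23 × 0.589 = 13.5 of 23.

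The range is therefore about 9 to 18 of 23, depending on how uveal melanoma experience transfers to clear cell sarcoma.

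**Step 5. Antihypertensives side by side.**

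| | Section 5.1.3 | Section 5.2 |
|---|---|---|
| Force | Investigator considers reducing or omitting | Should be held |
| Window | 24 hours before and after | 24 hours before and after |
| Period | A minimum of 3 weeks | First 6 weeks, then discretion |
| Rebound-prone patients | Discuss with cardiology and the Principal Investigator | Not mentioned |

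The periods can be reconciled, because a 3-week minimum does not exclude 6 weeks. What remains is a difference in force throughout, and unclear guidance for weeks 4 to 6. The protocol does not say how many patients take these drugs.

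**The case against.** The best defence is that Section 5.1.3 states a general default and Appendix B is the graded, event-specific rule to which Sections 5.2 and 6 send the reader. There is also textual support for treating the triggers as different events. Section 5.1.3 itself distinguishes CRS from infusion reactions when it sets the monitoring rule for the first six patients. Appendix B has a separate row for reactions during the infusion, and its Grade 2 premedication there (acetaminophen and an antihistamine) fits Section 5.1.3.

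Part of this stands. A reader is not left without direction, and an experienced site might well follow Appendix B. But the joint heading of the CRS row undoes the separation of events, and the pointers to Appendix B never say that it overrides Section 5.1.3. The precedence has to be inferred.

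Other objections also hold. That Appendix B does not mention consulting the Principal Investigator is not a conflict, since a site can do both. The cardiology discussion adds to Section 5.2 without opposing it. The Grade 2 CRS row already calls for high-dose steroids and/or tocilizumab when symptoms do not resolve quickly, and Section 7.3.1 has CRS managed by institutional protocol. Some variation in steroid use between sites would therefore remain after any correction.

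Three stronger readings are tempting and are not supported:

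- That most patients will face opposing instructions. This needs the uveal melanoma rates to carry over, and at half those rates it fails (9 of 23).
- That CRS is the protocol's most frequent risk. Section 7.3.2 gives acute skin reactions in 92.7%.
- That the trial's rule of 5 successes in 23 is compromised. Nothing in the protocol gives the size or direction of a steroid effect on progression-free status at 24 weeks.

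**Conclusion.** The inconsistency is real and stands in the current text. For an event that Appendix B classes as both an infusion-related reaction and CRS, one section says to avoid steroid premedication unless a non-steroid combination has failed, and the other says to give it before the next dose.

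On the assumption that IMCgp100-202 rates apply, about 77% of patients (about 18 of 23) would meet the Appendix B trigger; at half that rate, about 9 of 23. The inconsistency may affect CRS prevention and the conditions of drug exposure across sites. Its effect on the primary result cannot be derived from the protocol.

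The antihypertensive discrepancy is a minor, separate item: a difference in force, and uncertainty in weeks 4 to 6, for an unknown number of patients.

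This is an internal inconsistency with a bearing on safety. It is not a flaw in the choice of design, the endpoint or the decision rule. No view is taken here on which clinical rule is right.

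**What to change.** 1. Reconcile the premedication paragraph of Section 5.1.3 with the Grade 2 and Grade 3 CRS entries of Appendix B. State the rule once, have the other place refer to it, and say which text prevails. If the Section 5.1.3 sentence is meant only for reactions during the infusion, say so.
2. Reconcile the antihypertensive paragraphs of Sections 5.1.3 and 5.2 in the same way, covering both the force of the rule and weeks 4 to 6.
3. Leave the choice of each rule to the sponsor's clinical team.
4. Confirm that steroid premedication is captured by date, so that CRS can be described by steroid exposure. Section 5.2 already requires concomitant medications to be documented, but Section 4.1 limits the eCRF to endpoint and safety data, so capture in the database should be checked.

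Items 1 and 2 cost amendment wording only. Item 4 is a check; if dates of steroid premedication are not in the eCRF, it also needs a small database change.
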